The proposed study is a single-blinded randomized controlled trial studying use of TENS for pain control during initial dilator insertion prior to dilation and evacuation. The participants will be randomized in a 1:1 randomization scheme using opaque, sequentially numbered envelopes following consent. The experimental group will have an active TENS unit – Chattanooga Primera – and the control group will have a sham TENS unit. The sham TENS will be the same unit without the true TENS electrical connections. The true TENS unit consists of the active unit and electrode pads connected to the unit via direct wires. The sham group will be given the active unit and have electrode pads placed but without wire connections. These participants will be told the device is a wireless device. They will also be told they may or may not feel sensation from the TENS. This will allow the device to be powered on and run in the same manner as the active group, but will not allow for electrical transmission between the unit and electrodes.

Based on power calculations, 56 participants are needed to detect a 20mm difference in VAS score with a standard deviation of 30mm. This is based on both minimum clinically significant difference in pain scores as well as previous studies regarding pain during dilator insertion. We will attempt to recruit 70 patients to account for possible TENS unit misuse or study dropout.

Eligible patients will be 18 years of age or older and between 14 weeks and 23 weeks 6 days gestation who meet inclusion/exclusion criteria as listed below. Two electrodes will be placed in

STU#:

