the suprapubic area in the bilateral lower quadrants (as shown in the figure at right). The program that will be used is a high frequency (80Hz) program that runs for an hour in duration. It will be initiated 5 minutes prior to speculum placement. Participants will be instructed to increase the amplitude of the current as needed to provide analgesia but avoiding discomfort from the TENS stimulation. All participants will receive a paracervical block of 20mL 1% lidocaine with sodium bicarbonate followed by rigid dilation and dilator placement per standard cervical preparation protocol. Participants will complete 100mm VAS immediately following dilator placement. VAS is a 100mm line on sheet of paper with 0 being no pain and 100mm being worst pain of their life. The number of dilators, type of dilators, and use of adjunctive mifepristone/misoprostol will be according to providers' clinical judgement. Dilator placement will be performed by either Family Planning Fellow, PGY-3 OB/GYN resident, or Nurse Practitioner. All participants will receive prescriptions for twenty tablets of ibuprofen (600mg) and twelve tablets of hydrocodone/acetaminophen 5/325, which is the standard post-dilator insertion pain protocol for this clinic site. Participants will be allowed to leave prior to the end of the initial one-hour program. They will be sent home with instructions of how to run the TENS unit as needed for pain control.

Following the initial hour of use patients can re-activate the TENS unit as often as desired, using the same program. Participants will be given a log to record when TENS unit was used and whether additional pain medications were taken (attached). They will return their completed log and bring pill bottles on the day of surgery to confirm medications used.

Of note, in our practice a second set of cervical dilators is often placed 6 hours after first set in patients over 20 weeks gestation. During this placement the first set is removed, further rigid dilation is performed, and new dilators are placed per standard cervical preparation protocol. Pain score on 100mm VAS will be recorded following this dilator placement as well as a secondary outcome. Participants will run the TENS unit in the same manner as the initial dilator placement for dilator exchange.

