Data will be managed using REDCap. All data will either be entered directly into REDCap (with data collected on tablet) or will be entered manually by the primary investigator or research assistant. The paper forms and iPads will be stored in a locked cabinet in a locked office only accessible to the primary investigator and research assistant. All paper forms will be shredded in HIPAA bins following data entry.

Study participants will be compared on baseline characteristics using appropriate statistical methods depending on normal distribution (student t-test or chi-squared test) or non-normal distribution. Primary and secondary outcomes will be measured using appropriate statistical analyses for continuous or categorical data. A two-tailed p value of less than or equal to 0.05 will be considered statistically significant.

The number of subjects needed to show a 20mm reduction on VAS with a standard deviation of 30mm is 56, or 28 per arm. To account for subject discontinuation we will attempt to recruit 70 participants.

According to previous studies the minimum clinically significant difference in VAS is 15mm, however, this is within the standard deviation of typical VAS scores of pain during laminaria insertion and could confound study results. Soon et al previously used a 25mm reduction on VAS to calculate power in a previous study examining pain control during dilator insertion using paracervical block. We have chosen to use a 20mm reduction on VAS as this difference has shown significant in previous pain management research studies and we believe this to be a difference that will alter clinician practice patterns.

PROVISIONS TO MONITOR THE DATA TO ENSURE THE SAFETY OF PARTICIPANTS

This study does not involve more than minimal risk to the participants

PROVISIONS TO PROTECT THE PRIVACY INTERESTS OF PARTICIPANTS

On the day of their pre-operative abortion consultation appointment, a study team member will approach eligible patients regarding study enrollment. The questions they are asked regarding

STU#:

personal health information and demographics are questions that would be asked regardless of study participation.

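### The primary VAS analysis makes no stated use of gestational age, a baseline variable known at eligibility; prespecifying adjustment for it costs almost nothing and may recover some power

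*Combined protocol and SAP*

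**What the plan says.** The analysis text is in the Data Management and Confidentiality section. For the outcomes it reads: "Primary and secondary outcomes will be measured using appropriate statistical analyses for continuous or categorical data". The significance rule follows: "A two-tailed p value of less than or equal to 0.05 will be considered statistically significant". No test, model, covariate, effect measure or confidence interval is named for the primary VAS.

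The sentence just before it concerns something else: "Study participants will be compared on baseline characteristics using appropriate statistical methods depending on normal distribution". The choice of method according to distribution is written there, for baseline characteristics only.

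On allocation, Procedures Involved says: "The participants will be randomized in a 1:1 randomization scheme using opaque, sequentially numbered envelopes following consent". No stratification or blocking is described.

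The Inclusion and Exclusion Criteria make gestational age an eligibility item, so it is known before allocation. Procedures Involved also says: "Dilator placement will be performed by either Family Planning Fellow, PGY-3 OB/GYN resident, or Nurse Practitioner". It does not say when the provider for a given participant is assigned.

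The target effect is a mean VAS reduction of 20 mm (Objectives), and the sample size is built on it: "The number of subjects needed to show a 20mm reduction on VAS with a standard deviation of 30mm is 56, or 28 per arm".

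**The concern.** The eligible range covers nearly ten weeks of gestation, and the number and type of dilators are left to the provider. It is plausible, though not documented here, that placement pain varies with gestational age. If it does, an analysis that ignores gestational age leaves that variation in the error term.

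This trial has little power to spare. The same section of the protocol treats VAS variability as a limiting factor when it sets aside the 15 mm minimum clinically significant difference. Under the stated two-tailed 0.05, the planned 56 evaluable participants give about 69–70% power for 20 mm. A baseline variable that is already in hand and could reduce residual variance is worth using.

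Adjustment also has to be written down beforehand to be credible. As the text stands, an adjusted model, a t-test and a rank test would all count as appropriate, and a rank test would not estimate the 20 mm mean difference in the hypothesis.

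**Working it through.** **Inputs from the protocol.** Difference 20 mm, SD 30 mm, 28 per arm (56 evaluable), 70 recruited (35 per arm), two-tailed alpha 0.05. Power is not stated.

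**Inputs assumed.** R², the share of VAS variance explained by gestational age: 0 to 0.20 in the main table. The documents give no value.

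**Step 1: the plan's own figure.** n per arm = 2(z_alpha + z_beta)² × SD²/difference², with SD²/difference² = 900/400 = 2.25.

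- Two-sided 0.05, 80% power: 2 × (1.960 + 0.842)² × 2.25 = 35.3, so 36 per arm, 72 in total. This does not match.
- One-sided 0.05, 80% power: 2 × (1.645 + 0.842)² × 2.25 = 27.8, so 28 per arm, 56 in total. This matches.
- Two-sided 0.05, 70% power: 2 × (1.960 + 0.524)² × 2.25 = 27.8, so 28 per arm, 56 in total. This also matches.
- Recruitment: 56/0.80 = 70, so the target allows for 20% loss.

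**Step 2: power without adjustment, two-sided 0.05.** Noncentrality = 20/(30 × √(2/n)).

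- n = 28: 2.494, giving 68.8% by noncentral t on 54 df (70.3% by normal approximation).
- n = 35: 2.789, giving 78.5% on 68 df (79.6% by normal approximation).

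**Step 3: power with gestational age as one linear covariate.** Residual SD = 30 × √(1 − R²). The error df fall by 1. The variance of the arm difference is multiplied by the expected inflation from chance covariate imbalance, 1 + 1/(N − 4), which is 1.0192 at N = 56 and 1.0152 at N = 70. Noncentrality = 20/(residual SD × √(2/n × inflation)).

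| Analysis | Residual SD (mm) | Power, N = 56 | Power, N = 70 |
|---|---|---|---|
| Unadjusted | 30.00 | 68.8% | 78.5% |
| Adjusted, R² = 0 | 30.00 | 67.9% | 77.9% |
| Adjusted, R² = 0.10 | 28.46 | 72.5% | 82.0% |
| Adjusted, R² = 0.20 | 26.83 | 77.4% | 86.2% |

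The change against the unadjusted test is −0.9, +3.7 and +8.6 points at N = 56, and −0.6, +3.5 and +7.7 points at N = 70. Break-even is at R² of about 0.02 for either N. Reaching 80% with 56 evaluable would need R² of about 0.25.

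**Step 4: adding provider type.** Three categories add 2 df, so 3 covariate df in all, and the inflation becomes 1 + 3/(N − 6). Here R² is the share explained by both variables together.

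| R² | Power, N = 56 | Power, N = 70 |
|---|---|---|
| 0 | 66.2% | 76.6% |
| 0.10 | 70.7% | 80.8% |
| 0.20 | 75.7% | 85.1% |

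Break-even moves to about 0.06 (N = 56) and 0.05 (N = 70).

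**The case against.** The strongest reply is that the benefit rests on a correlation the documents never report. If gestational age is unrelated to placement pain, adjustment gains nothing, and a prespecified t-test with a confidence interval would be a respectable primary analysis. The first part stands: R² is an assumption throughout. But with one covariate the two sides are unequal, a loss of under 1 point against a gain of about 3.5 to 9 points over the assumed range.

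Several stronger readings are tempting and do not hold.

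- A reader might infer that the primary VAS is assigned an unadjusted test chosen after inspecting normality. The distribution-dependent wording belongs to the baseline comparison; the primary method is simply not named.
- A reader might infer that the envelopes are known to be unstratified and that chance imbalance in gestational age would bias the result. Stratification is not described, but neither is it excluded. Chance imbalance under randomisation is not bias, and the unadjusted confidence interval already allows for it (half-width about 1.995 × 30 × √(2/35) = 14.3 mm with all 70 evaluable).
- A reader might count the dilator exchange as a source of variation in the primary outcome. It takes place about 6 hours after the first set, whereas the primary VAS is taken immediately after the initial placement. It bears on secondary outcomes only.
- A reader might treat provider type as equally safe to adjust for. The documents do not show that it is fixed before allocation, and it is not in the list of investigative procedures. The active and sham set-ups differ visibly in their wiring, so an assignment made after allocation could be influenced by arm. Dilator number and type raise the same difficulty.

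**Conclusion.** The point holds in a limited form. The primary analysis is unspecified, and gestational age, which is available at eligibility, has no stated role in randomisation or analysis. Prespecified adjustment for it is a better method than leaving it out, at a cost of one degree of freedom and less than 1 point of power in the worst case.

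The size of the gain is conditional. With R² of 0.10–0.20 (assumed), power goes from 68.8% to about 72–77% at 56 evaluable, and from 78.5% to about 82–86% at 70. These figures also rest on the protocol's 30 mm SD and on a linear relation with gestational age.

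It would be wrong to conclude that adjustment is free or that it repairs the sample size. With 56 evaluable, power stays below 80% throughout that range. The shortfall comes from a figure of 56 that matches one-sided 0.05 with 80% power, or two-sided 0.05 with 70% power, and it needs its own answer.

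**What to change.** In Data Management and Confidentiality, state before any outcome data are seen that:

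- the primary analysis is a linear model of VAS on arm and continuous gestational age, reporting the adjusted mean difference in mm with a 95% confidence interval from robust standard errors;
- the unadjusted mean difference is reported as a sensitivity analysis;
- provider type enters the model only if it is fixed and recorded before the envelope is opened, and dilator number and type are not adjusted for unless the same is true of them.

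The cost is a short paragraph and one degree of freedom, with no added participants or visits. Gestational age is already established at eligibility; the team need only confirm that it is carried into the study database. Adding provider type would require a pre-allocation record and would raise the worst-case loss to about 2–3 power points.

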STU#:

PROTOCOL TITLE: Transcutaneous electrical nerve stimulation (TENS) for pain control during cervical dilator placement prior to dilation and evacuation: A randomized controlled trial

PRINCIPAL INVESTIGATOR:

[name], MPH
[name]
[name]
[name]
Department of OB/Gyn
[contact]

VERSION NUMBER:

1

VERSION DATE:

12/4/18

STUDY SUMMARY:

Investigational Agent(s) (Drugs or Devices)	Primera TENS/NMES Unit with HAN Waveform by Chattanooga
IND / IDE / HDE #	
Indicate Special Population(s)	 Children  Children who are wards of the state  Adults Unable to Consent  Cognitively Impaired Adults  Neonates of Uncertain Viability  Pregnant Women  Prisoners (or other detained/paroled individuals)  Students/Employees
Sample Size	70
Funding Source	Society of Family Planning Research Fund
Indicate the type of consent to be obtained	 Written  Verbal/Waiver of Documentation of Informed Consent  Waiver of HIPAA Authorization  Waiver/Alteration of Consent Process
Site	 Lead Site (For A Multiple Site Research Study)  Data Coordinating Center (DCC)
Research Related Radiation Exposure	 Yes  No
DSMB / DMC / IDMC	 Yes  No

STU#:

OBJECTIVES:

- Primary Outcome: Self-reported pain on 100mm VAS immediately following dilator placement
- Secondary Outcomes:
 - Self-reported pain at dilator exchange (if applicable)
 - Amount of time (in minutes) spent in clinic following dilator insertion
 - Self-reported highest level of pain between dilator placement and D&E
 - Number and type of adjunctive pain medications used
 - Patient acceptability

The hypothesis is that use of TENS will decrease pain by 20mm on VAS during initial dilator placement prior to dilation and evacuation, improving patient's overall pain management

BACKGROUND:

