4. Lack of sensation to touch on area of electrode placement
5. Prior TENS use
6. Opioid dependence

All patients between 14 weeks and 23 weeks 6 days gestation who schedule an appointment for a Dilation and Evacuation procedure with Northwestern Family Planning will be reviewed for study eligibility by the study team. All patients will be asked by clinical staff when scheduling an appointment if they have an implanted cardiac device or have used a TENS unit in the past. If eligibility criteria are met, then the patient will be approached regarding this study during the initial consultation appointment following description of dilator insertion procedure.

VULNERABLE POPULATIONS

The population being studied is pregnant women who have previously decided to have a termination of pregnancy or have an intrauterine fetal demise. They will confirm their decision for termination and consent to the termination procedure prior to being approached for study participation and subsequent TENS unit placement. TENS units have previously been studied

STU#:

during labor without adverse effects on the fetus. Therefore, the only potential risk would be patient discomfort from the TENS or allergic reaction to the electrode pads. These risks are rare and short-lived. Any fetal risk that has not previously been identified would be insignificant, as termination of pregnancy will occur 24-36 hours later.

PARTICIPANT POPULATION(S)

Accrual Number:	Category/Group: (Adults/Children Special/Vulnerable Populations)	Consented: Maximum Number to be Consented or Reviewed/Collected/Screened	Enrolled: Number to Complete the Study or Needed to Address the Research Question
Local	Pregnant Women	70	70
Study-wide			
Total:		70	70

RECRUITMENT METHODS

Study participants will be recruited at the Family Planning Clinic at Northwestern Memorial Hospital in Chicago, IL. This study will be registered with ClinicalTrials.gov per protocol. Participation will be completely voluntary. The Family Planning Clinic population is highly variable and includes patients with both Medicaid and private insurance. It includes patients referred from the greater Chicagoland area as well as from nearby states with more prohibitive abortion legislation. This clinic performs about 400 dilation and evacuation procedures requiring dilator placement per year.

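### The 56 participants said to be needed give only about 69% power under the plan's own two-tailed 0.05 rule, and the plan does not state the power or sidedness behind the figure

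*Combined protocol and SAP*

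**What the plan says.** The sample size is justified in two places. Under Procedures Involved: "Based on power calculations, 56 participants are needed to detect a 20mm difference in VAS score with a standard deviation of 30mm". Under Data Management and Confidentiality: "The number of subjects needed to show a 20mm reduction on VAS with a standard deviation of 30mm is 56, or 28 per arm". Allocation is 1:1.

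The recruitment target is 70. Data Management and Confidentiality gives the reason: "To account for subject discontinuation we will attempt to recruit 70 participants". Procedures Involved also cites possible misuse of the unit. Neither section gives a loss rate.

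The only statement about the significance test is in Data Management and Confidentiality: "A two-tailed p value of less than or equal to 0.05 will be considered statistically significant". The hypothesis under Objectives is directional ("The hypothesis is that use of TENS will decrease pain by 20mm on VAS during initial dilator placement"), but no section mentions a one-sided test. No section states the target power, the alpha and sidedness used to size the trial, or the formula.

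The accrual table under Participant Population(s) enters 70 in the column headed "Enrolled: Number to Complete the Study or Needed to Address the Research Question".

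**The concern.** A statement that a given number is needed to detect a given effect means little unless the power is stated, and most readers will assume at least 80%. With a 20 mm difference and SD 30 mm, 28 per arm looks too small for 80% power in a two-sided test at 0.05.

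This is the sample size justification for the primary outcome. If only 56 participants are evaluable and TENS truly lowers the score by 20 mm, about 3 in 10 such trials would not reach significance, and the device could be read as ineffective. The plan gives no sign that this risk was recognised or accepted.

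**Working it through.** **Inputs.** Difference 20 mm, SD 30 mm and 28 per arm (Data Management and Confidentiality); 1:1 allocation (Procedures Involved); two-tailed alpha 0.05 (Data Management and Confidentiality). The standardised effect is 20/30 = 0.667. Power is not stated; 80% is assumed below as the conventional target, and 70%, 85% and 90% were also tried. The plan names no primary test beyond a method suited to the data type, so a two-sample t-test is assumed, with the normal approximation alongside.

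**Reproducing 28 per arm.** Normal approximation: n per arm = 2 × (z_alpha + z_power)² × (SD/difference)², where 2 × (30/20)² = 4.5.

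- One-sided 0.05, 80% power: 4.5 × (1.645 + 0.842)² = 27.8, so 28 per arm, 56 in total. Match.
- Two-sided 0.05, 70% power: 4.5 × (1.960 + 0.524)² = 27.8, so 28 per arm, 56 in total. Match.
- Two-sided 0.05, 80% power: 4.5 × (1.960 + 0.842)² = 35.3, so 36 per arm, 72 in total. No match.
- Two-sided 0.05, 85% and 90% power: 41 and 48 per arm. No match.
- One-sided 0.05, 70%, 85% and 90% power: 22, 33 and 39 per arm. No match.

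Two sets of assumptions therefore give the plan's figure, and the documents do not say which was used. By t-test the one-sided 80% requirement is 28.5, so 29 per arm; the match to 28 holds under the normal approximation.

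**Power under the declared rule.** Normal approximation: power = Φ(0.667 × √(n/2) − 1.960). The t-test column uses the noncentral t distribution.

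| Evaluable per arm | Total | Two-sided power, t-test | Two-sided power, normal |
|---|---|---|---|
| 28 | 56 | 68.8% | Φ(2.494 − 1.960) = 70.3% |
| 35 | 70 | 78.5% | Φ(2.789 − 1.960) = 79.6% |
| 36 | 72 | 79.7% | 80.7% |
| 37 | 74 | 80.8% | 81.8% |

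For comparison, one-sided power at 28 per arm is 79.3% (t-test) or 80.2% (normal).

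**Detectable difference at 80% power (two-sided t-test, SD 30 mm).** 22.9 mm with 28 per arm and 20.4 mm with 35 per arm. With 28 per arm, 20 mm is detectable at 80% power only if the SD is about 26.2 mm or less.

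**The recruitment target.** 70 − 56 = 14, and 14/70 = 20%. The plan does not state this rate; it is only what the two numbers imply.

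**The case against.** **Was it a sidedness error?** A reader might infer that 28 per arm is a one-sided sample size at 80% power, wrongly paired with a two-tailed test. The documents do not support stating this as fact. They give no target power, one-sided alpha or formula, and the only sidedness they mention is two-tailed. Two-sided 0.05 at 70% power gives the same 28 and does not conflict with the declared test. The one-sided account is the likelier one, because 80% is conventional and nothing suggests that 70% was chosen, but it remains an inference. This objection stands as to the cause. It does not clear the plan: on one account the calculation contradicts the declared test, and on the other the plan calls 56 the number needed without disclosing a 30% chance of missing its target effect.

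**Is 69% too pessimistic?** It is the lower end. The primary score is taken in clinic straight after placement, and under Withdrawal of Participants those who fail to provide later data remain in the primary analysis. Loss for the primary outcome would come mainly from stopping TENS during placement, pad allergy or withdrawal, so the evaluable number may exceed 56. This stands, and the fair range is 69% (56 evaluable) to 78.5% (all 70). But the 14 extra participants are there to cover losses, and even with none, 70 is just below 72 to 74.

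**Does the plan claim a 20% reserve?** A reader might infer a planned 20% loss. The plan states no rate, so there is no such claim to withdraw.

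**Does the accrual table contradict the calculation?** Only weakly. The column heading covers both completing the study and answering the research question, and 70 in both columns may be no more than loose form-filling. It needs tidying and has no bearing on the power.

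**Conclusion.** The point holds as a statement about undisclosed and low power. With 20 mm, SD 30 mm, 1:1 allocation and the two-tailed 0.05 rule, 56 evaluable participants give about 69% power by t-test (70% by normal approximation), and all 70 would give about 78.5%. Conventional 80% power needs 72 to 74 evaluable, which is 16 to 18 more than the number the plan says it needs.

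The power figures at 56 and 70 follow from the plan's own inputs, plus the assumption of a t-test or its normal approximation. The shortfall of 16 to 18 also rests on taking 80% as the benchmark, which the plan does not state. The origin of 28 per arm is not established, and the conclusion does not depend on it.

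**What to change.** Keep the two-tailed test; do not make it one-sided to rescue the number. In both Procedures Involved and Data Management and Confidentiality, replace the sample size statement with wording such as:

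*With two-sided alpha 0.05 and SD 30 mm, 56 evaluable participants give about 69% power and 70 give about 78% power to detect 20 mm (detectable difference at 80% power: 22.9 mm and 20.4 mm); 80% power for 20 mm would need 72 to 74 evaluable.*

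State the power, alpha and sidedness that the original calculation used. As a minor item, make the 70 in the accrual table agree with the 56 given as needed elsewhere, for example by labelling 70 as the recruitment target.

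The cost is a change of wording and a less favourable stated power. No extra enrolment is required. If the sponsor prefers to secure 80% power, the target becomes 72 to 74 evaluable; at the 20% loss implied by 56/70 that means recruiting 72/0.8 = 90 to 74/0.8 = 92.5, rounded up to 94 for equal arms.
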